#### **Regression models**

Models will be checked using graphic inspection of diagnostic plots. Splines will be used to account for non-linear effects, and interactions will be included in the model based on relevant subject-matter knowledge. The coefficient of determination, adjusted R-squared, will illustrate the percentage of variance in PA that is explained by the predictive variables. The higher the coefficient, the stronger the relationship. The root mean squared error of the estimate will indicate the accuracy of the predictions.

The following models will be applied:

- Model 1
  - a) Multiple linear regression analysis between accelerometer counts (response variable) and all CPUP variables within each ICF component (predictive variables), using the latest CPUP registration prior to accelerometer data collection.
  - b) Multiple linear regression analysis between accelerometer counts (response variable) and all questionnaire variables within each ICF component (predictive variables), using the questionnaire data.
- Model 2
  - a) Penalized regression (lasso) with accelerometer counts as the response variable and covariates as chosen by lasso to obtain an optimal fit from model 1a as predictive variables to determine which variables to retain in the model.
  - b) Penalized regression (lasso) with accelerometer counts as the response variable and covariates as chosen by lasso to obtain an optimal fit from model 1b as predictive variables to determine which variables to retain in the model.

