#### Study size

The expected study size of 300-400 children, as mentioned in the protocol article, was obtained for consent given to participate. However, due to the COVID-19 pandemic, and consequences thereof, accelerometer data was only obtained for 123 children. Furthermore, due to the incompleteness of registered children in the CPUP database, only 78 of these children are eligible for analysis with CPUP data.

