### Protocol deviations

Due to the COVID-19 pandemic and related shutdown of schools and after school activities, data collection was hindered and thus resulted in a reduced number of expected participants. Thus, deviations to protocol (as published (1), and initially registered at ClinicalTrials.gov November 3, 2020) are as follows:

- Data collection ended January 31st 2022
- It is not a requirement for the children to be registered in the CPUP
- Primary analysis: Due to a relatively large amount of included children not being registered in the CPUP, additional analyses will be performed on all children with accelerometry data (Model 1b):
  - o Model 1
    - a) Multiple linear regression analysis between accelerometer counts (response variable) and all CPUP variables within each ICF component (predictive variables), using the latest CPUP registration prior to accelerometer data collection.
    - b) Multiple linear regression analysis between accelerometer counts (response variable) and all questionnaire variables within each ICF component (predictive variables), using the questionnaire data.
- Secondary analysis. Due to the limited amount of children and adolescents included in the study, the protocol's model 2a (backward stepwise regression with accelerometer counts as the response variable and all included CPUP variables as predictive variables) will be performed for both model 1a and 1b using penalized regression. Furthermore, the initial model 2b (Multiple linear regression analysis between accelerometer counts (response variable) and all included variables as predictive variables) will be eliminated:
  - o Model 2
    - a) Penalized regression (lasso) with accelerometer counts as the response variable and covariates as chosen by lasso to obtain an optimal fit from model 1a as predictive variables to determine which variables to retain in the model.
    - b) Penalized regression (lasso) with accelerometer counts as the response variable and covariates as chosen by lasso to obtain an optimal fit from model 1b as predictive variables to determine which variables to retain in the model.

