### Missing data

Missing outcome data (accelerometer data) will exclude the child from the study population. Missing data on predictors (CPUP and questionnaire data, including personal factors) will be handled by multiple imputation by multivariate imputation using chained equation (MICE) including all predictors and 100 imputation samples.

In model 2a and 2b the imputation will be performed before applying the lasso, and afterwards the predictors will be ordered by proportion of imputation sets in which they are included. From this prioritized list, we will construct a final prediction model including all predictors included in at least 50% of the

imputation sets, but other cutoffs than 50% will be evaluated by an elbow plot, and if a different cutoff appears convincing from the plot, this cutoff will be applied.

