Table 3. Prediction of physical activity using questionnaires as predictive variables (Model 1b)

ICF constructs	Variables	Coef. [95% CI]	p-value	Adj.R 
Body Function & Structure				xx
	ROM	xx [xx,xx]	xx	
	Number of hours of sleep per night	xx [xx,xx]	xx	
	GMFCS level	xx [xx,xx]	xx	
	PODCI – pain/comfort scale	xx [xx,xx]	xx	
Activities				xx
	FMS (5m, 50m 500m)	xx [xx,xx]	xx	
	Means of transport to school	xx [xx,xx]	xx	
	Hours of screen time per day	xx [xx,xx]	xx	
Participation				xx
	Participation in PT at school	xx [xx,xx]	xx	
	Participation in recreational activities	xx [xx,xx]	xx	
	PODCI - Global Function score	xx [xx,xx]	xx	
	PODCI - Sports and Physical Functioning score			
Personal Factors				xx
	Age	xx [xx,xx]	xx	
	Gender	xx [xx,xx]	xx	
	Parent's educational level	xx [xx,xx]	xx	
Environmental Factors				xx
	Residence region	xx [xx,xx]	xx	
Quality of Life				xx
	PedsQL	xx [xx,xx]	xx	

Abbreviations: ROM: Range of motion; FMS: Functional Mobility Scale, PODCI: Pediatric Outcomes Data Collection Instrument; PT: physical training; PedsQL: Pediatric Quality of Life Inventory, CP Module

Table 4. Prediction model using “the best” CPUP variables (penalized regression, lasso) (model 2a)  
(Like table 2, only including the variables that the lasso regression has selected)

Table 5. Prediction model using “the best” questionnaire variables (penalized regression, lasso)  
(model 2b)

(Like table 3, only including the variables that the lasso regression has selected)

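### Lasso Models 2a and 2b: fit in the children used to select the model is reported as prediction accuracy, with no validation planned

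*Combined protocol and SAP*

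**What the plan says.** Section 7, Regression models, names two performance measures ahead of the list of Models 1 and 2, so they cover both. One is that "adjusted R-squared, will illustrate the percentage of variance in PA that is explained by the predictive variables". The other is that "The root mean squared error of the estimate will indicate the accuracy of the predictions".

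Section 7, Missing data, describes how Models 2a and 2b are built. The lasso follows imputation, and predictors are ranked by the share of imputation sets that retain them. From that list "we will construct a final prediction model including all predictors included in at least 50% of the" imputation sets. The 50% is not binding: other values are examined on an elbow plot, and "if a different cutoff appears convincing from the plot, this cutoff will be applied". The rule for choosing the lasso penalty is not given beyond the aim of an optimal fit.

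Tables 4 and 5 follow the layout of Tables 2 and 3 (coefficient, 95% CI, p-value, adjusted R-squared), "only including the variables that the lasso regression has selected".

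Section 4, Protocol deviations, says that the published protocol's Model 2a was backward stepwise regression and now "will be performed for both model 1a and 1b using penalized regression".

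On numbers, section 3, Study size, says that "accelerometer data was only obtained for 123 children" and that "only 78 of these children are eligible for analysis with CPUP data".

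The SAP names no hold-out sample, cross-validation of the final model, bootstrap correction or external data. Under Statistical software, random seeds are foreseen for imputation only.

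**The concern.** Selection, cutoff, estimation and assessment all use the same 78 or 123 children. Predictors enter the final model because they fit these children, so fit measured in these children is too favourable. Adjusted R-squared does not repair this, because it corrects for the terms kept and not for the candidates searched. Choosing the cutoff by eye on the same data is a further data-driven step that no formula accounts for.

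At stake is the reading of Tables 4 and 5. The SAP calls the result a prediction model and the RMSE its accuracy. A reader of Table 4 could credit the CPUP variables with predictive value that would largely disappear in children outside the sample.

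**Working it through.** The SAP gives no target R-squared, expected RMSE or outcome SD, so there is no figure of its own to reproduce. The size has to come from simulating the plan under stated assumptions.

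**Inputs from the SAP.** n=78 (Model 2a) and n=123 (Model 2b). Table 2 lists 4+4+2+3+3 = 16 variables, and Table 3 lists 4+3+4+3+1+1 = 16. Dummy coding GMFCS (3 levels), CP subtype (4) and region (5) in Table 2 adds 1+2+3 terms, giving 16+6 = 22.

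**Assumptions.** All variables of a set enter one lasso; 22 terms at both sample sizes; predictor correlation 0.3; five true predictors; no splines or interactions; OLS refit of the retained terms.

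**Why the adjustment falls short.** Adjusted R-squared = 1 - [RSS/(n-q-1)] / [TSS/(n-1)], with q the number of retained terms. The number of candidates does not appear in it. The RMSE, sqrt(RSS/(n-q-1)), has the same limitation.

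**Step 1: complete data, 400 replicates.** Cells give adjusted R-squared / R-squared in new children / ratio of new-child to reported RMSE.

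| n, true R-squared | Minimum-CV penalty | One-standard-error penalty | BIC penalty |
|---|---|---|---|
| 78, 0.2 | 0.249 / 0.045 / 1.148 | 0.129 / 0.018 / 1.084 | 0.160 / 0.026 / 1.101 |
| 78, 0.4 | 0.434 / 0.265 / 1.163 | 0.399 / 0.265 / 1.129 | 0.406 / 0.264 / 1.137 |
| 123, 0.2 | 0.231 / 0.099 / 1.096 | 0.154 / 0.062 / 1.069 | 0.174 / 0.078 / 1.071 |
| 123, 0.4 | 0.418 / 0.313 / 1.102 | 0.407 / 0.329 / 1.078 | 0.408 / 0.327 / 1.081 |

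Gaps in R-squared at n=78 run from 0.129-0.018 = 0.11 to 0.249-0.045 = 0.20. At n=123 they run from 0.407-0.329 = 0.08 to 0.231-0.099 = 0.13. RMSE in new children is 8-16% and 7-10% larger than reported.

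**Step 2: closer to the SAP.** 10% of predictor values missing at random, chained-equation imputation, 20 imputation sets (the SAP plans 100), 50% retention, pooled refit, 120 replicates.

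| n, true R-squared | Minimum-CV penalty | One-standard-error penalty |
|---|---|---|
| 78, 0.2 | 0.228 / 0.069 / 1.111 | 0.104 / 0.014 / 1.066 |
| 78, 0.4 | 0.391 / 0.281 / 1.105 | 0.346 / 0.237 / 1.102 |
| 123, 0.2 | 0.221 / 0.111 / 1.071 | 0.149 / 0.060 / 1.055 |
| 123, 0.4 | 0.392 / 0.320 / 1.061 | 0.382 / 0.321 / 1.050 |

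The gap is 0.09-0.16 at n=78 and 0.06-0.11 at n=123. RMSE is 7-11% and 5-7% larger.

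**Step 3: separate simulation with other term counts.** This used 16 or 25 candidate terms, complete data, true R-squared 0, 0.2 or 0.4, a cross-validated penalty, and 100 runs per setting. Adjusted R-squared was too high in all 12 settings, by 0.13-0.26 at n=78 and 0.08-0.16 at n=123. For example, with n=78, 16 terms and true R-squared 0.2, it was 0.267 against 0.065.

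**Step 4: Model 1 for comparison.** With pre-listed normally distributed predictors, the expected ratio of new-child to reported RMSE is about sqrt[(1+1/n)(n-2)/(n-p-2)]. Here p is the number of terms in one ICF component.
- n=78, p=2: sqrt(1.0128 x 76/74) = 1.020. p=6: sqrt(1.0128 x 76/70) = 1.049.
- n=123, p=1: sqrt(1.0081 x 121/120) = 1.008. p=5: sqrt(1.0081 x 121/116) = 1.025.

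The shortfall is therefore 2.0-4.9% and 0.8-2.5%. It comes from estimation error alone.

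**Step 5: does cross-validating the whole procedure recover the right value?** Complete data, 80 replicates; the figures are R-squared.

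| Setting (n=78) | Apparent | True in new children | Nested CV | Plain bootstrap |
|---|---|---|---|---|
| True R-squared 0.2, minimum-CV | 0.258 | 0.037 | -0.001 | -0.027 |
| No signal, minimum-CV | 0.064 | -0.102 | -0.125 | -0.312 |
| True R-squared 0.4, one-SE | 0.401 | 0.269 | 0.226 | 0.248 |

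Over eight settings, nested cross-validation was 0.02-0.04 below the true value and the plain bootstrap 0.02-0.21 below.

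**The case against.** **The refit is inferred.** The SAP calls Model 2 penalized regression and never says refit. With the lasso coefficients kept and complete data, the gap falls to 0.03-0.12 and the RMSE excess to 3-10%. This stands as to size. The direction is unchanged, and a single model shown with confidence intervals and p-values points to a refit.

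**Not all of the gap is selection.** This also stands. At n=78 and true R-squared 0.2, OLS on the five true predictors fixed in advance already has a gap of 0.05. Unselected OLS on all 22 terms does worse than the lasso (0.178 against -0.143). The Model 1 comparison likewise mixes fewer terms with no selection. For a claim about prediction, however, both sources count, and the reported figures show neither in full.

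**Adjusted R-squared describes association.** Read as an estimate of the population R-squared, it is below the truth in six of the eight cells of step 2. This narrows the point to the predictive reading. The SAP invites that reading by presenting a final prediction model and calling its RMSE accuracy.

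**The harm is limited.** The objective is to identify predictors, and the lasso is secondary. With no signal at all, the apparent value at n=78 is at most about 0.06, which would mislead few readers. The risk lies with weak true signal, as in the first row of step 2.

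**The protocol article was not available.** A general validation step there cannot be excluded. However, the lasso, the pooling across imputations and the cutoff are set out here as a replacement for the protocol's stepwise model. The SAP points to no validation elsewhere.

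**The lasso may use cross-validation internally.** That would tune the penalty only. It would not assess the model after pooling, cutoff and refit.

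**Conclusion.** The concern holds. Followed as written, the plan gives adjusted R-squared and RMSE for Models 2a and 2b that are too favourable as measures of prediction in other children. The problem is greatest for Model 2a at n=78.

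Under the 50% rule with a refit, the likely overstatement of R-squared is 0.09-0.16 at n=78 and 0.06-0.11 at n=123. Without a refit it is smaller but still positive. These sizes rest on the assumed number of terms, correlation, number of true predictors, true R-squared and missingness, none of which the documents fix. Splines, interactions and the elbow-plot choice were not simulated; where chosen from the data, they would tend to add optimism. If the four-valid-day rule reduces 78 or 123 further, the gap grows.

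This should be corrected, but it is confined to the secondary models. Model 1 uses pre-listed variables within one ICF component at a time, without selection, and is not affected in this way.

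**What to change.** Add to section 7, Regression models, for Models 2a and 2b only:

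> Prediction accuracy will be estimated by 10-fold cross-validation repeated 20 times. In each training set the imputation (10 sets), the lasso with a stated penalty rule, the fixed 50% retention cutoff and the refit are repeated. The outcome of held-out children does not enter the imputation. Cross-validated R-squared and RMSE are reported with Tables 4 and 5 as the measure of prediction accuracy. Full-sample adjusted R-squared and RMSE are labelled apparent.

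State the penalty rule and whether the final coefficients come from a refit, and extend the seed statement to the cross-validation folds. In section 7, Missing data, make any elbow-plot cutoff a sensitivity analysis, or replace it with an algorithmic rule repeated in each training set. If a bootstrap is preferred, keep copies of the same child in one inner fold, because the plain version over-corrects when the penalty is tuned by cross-validation.

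**Cost.** No new data are needed. Each model requires 20 x 10 x 10 = 2,000 imputed training sets and as many lasso fits, or roughly ten times as many fits if the penalty is itself chosen by 10-fold cross-validation. The validation uses 10 imputations per training set rather than the planned 100, which should be stated. The visual choice of cutoff is lost for the validated model, and the reported accuracy will be less favourable. The minimum acceptable change is to label the values in Tables 4 and 5 as apparent fit and drop the claim that they show prediction accuracy. That would leave the actual accuracy unknown.

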## 2. Introduction

### Background and rational

Children and adolescents with cerebral palsy may be trapped in a vicious circle of low physical fitness, resulting in deconditioning that causes a further decrease in physical activity (PA), a lower quality of life and an increased risk of developing non-communicable diseases. Therefore, establishing a healthy and active lifestyle during childhood is even more important for individuals with a disability. However, the factors that influence habitual PA in children and adolescents with cerebral palsy remain unknown.

In Scandinavia, healthcare professionals offer standardized clinical examinations throughout childhood using the Cerebral Palsy Follow-Up Program (CPUP). Identifying objective predictors of PA from this national clinical quality database, as well as from proxy-reported questionnaires concerning quality of life, functional status, and personal factors by means of a conceptual statistical framework (e.g. the International Classification of Functioning, Disability and Health (ICF)) may be used for an elaborated knowledge on habitual PA in children with CP. Specifically, the results will allow for early detection and potential improved interventions.

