### Study diagram

\*Latest CPUP registry entry, pre accelerometry collection, will be used as predictor variables for Model 1a + 2a.

\*\*Questionnaire data will be used as predictor variables for Model 1b + 2b.

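### Missing CPUP items could be imputed more precisely in Models 1a/2a if the child's own earlier value of the same item entered the imputation model, which the SAP does not plan

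*Combined protocol and SAP*

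**What the plan says.** The operative text is the Missing data section of the SAP. It foresees incomplete CPUP items: "Missing data on predictors (CPUP and questionnaire data, including personal factors) will be handled by multiple imputation". The method is "multivariate imputation using chained equation (MICE) including all predictors and 100 imputation samples". No auxiliary variable is named there, and neither is the outcome.

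Which CPUP value counts as the predictor is fixed elsewhere. Regression models specifies Model 1a "using the latest CPUP registration prior to accelerometer data collection", and the note to the Study diagram repeats it: "Latest CPUP registry entry, pre accelerometry collection, will be used as predictor variables for Model 1a + 2a".

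The Background describes a repeated examination: "healthcare professionals offer standardized clinical examinations throughout childhood using the Cerebral Palsy Follow-Up Program (CPUP". The word latest itself implies that a child can have more than one registration. Under Study size, "accelerometer data was only obtained for 123 children" and "only 78 of these children are eligible for analysis with CPUP data".

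**The concern.** When a clinical item is missing at one visit, the same item measured in the same child at an earlier visit is often the most informative available predictor of it. An analyst following the SAP as written would impute a missing GMFM-66 or muscle-tone value from the other predictors and would have no planned reason to retrieve the earlier registration. Doing so later would be an unplanned choice.

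What is at stake is precision in the smaller of the two analysis sets. Each missing item adds between-imputation variance to its coefficient, and a better-informed imputation adds less. The confidence intervals in Tables 2 and 4 for incomplete CPUP items would be somewhat wider than the registry allows.

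**Working it through.** **No figure to reproduce.** The SAP states no precision, power or missingness figure. The size has to come from simulation under stated assumptions.

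**Inputs from the documents.** n = 78 for Models 1a/2a (Study size); CPUP value from the latest registration; MICE with the predictors; two-sided alpha 0.05.

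**Assumptions not in the documents.** Share of children missing the item; correlation between earlier and latest value; share of children with an earlier value; correlation among predictors; missing completely at random; continuous items.

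**Step 1: base simulation.** n = 78, four predictors with pairwise correlation 0.3, true coefficient 0.30 for the incomplete item, 20 imputations, 600 replicates, an earlier value for every child, outcome in the imputation model. Pooling is by Rubin's rules: total variance = mean within-imputation variance + (1 + 1/M) × between-imputation variance. Mean standard error (SE) of the affected coefficient:

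| Missing | Correlation | SE without earlier value | SE with | Reduction |
|---|---|---|---|---|
| 5% | 0.5 / 0.7 / 0.9 | 0.105 / 0.106 / 0.105 | 0.104 / 0.105 / 0.104 | about 1% each |
| 10% | 0.5 / 0.7 / 0.9 | 0.108 / 0.108 / 0.108 | 0.108 / 0.106 / 0.105 | 0 / 2 / 3% |
| 20% | 0.5 / 0.7 / 0.9 | 0.114 / 0.114 / 0.114 | 0.112 / 0.110 / 0.106 | 2 / 4 / 7% |
| 40% | 0.5 / 0.7 / 0.9 | 0.131 / 0.131 / 0.133 | 0.128 / 0.123 / 0.114 | 2 / 6 / 14% |

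Reduction = 1 − SE with / SE without; for example 1 − 0.114/0.133 = 0.143.

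**Step 2: stronger correlation among predictors.** With pairwise correlation 0.5 and earlier-value correlation 0.8 and 0.9, the SE falls from 0.147 to 0.142 and from 0.148 to 0.139 at 20% missing (3% and 6%). At 40% missing it falls from 0.168 to 0.155 and from 0.170 to 0.147 (8% and 14%).

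**Step 3: incomplete availability.** With earlier values for 60 to 100% of children and correlation 0.5 to 0.9, the reduction is about 1-4% at 10% missing, 1-6% at 20% and 3-14% at 40%. This agrees with Step 1 to about one percentage point. As an equivalent gain in children for that one coefficient, 1/(1 − r)² − 1:
- 10% missing: 1/0.99² to 1/0.96², or 2-9%
- 20% missing: 1/0.99² to 1/0.94², or 2-13%
- 40% missing: 1/0.97² to 1/0.86², or 6-35%

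**Step 4: questionnaire counterpart also in the imputation.** Suppose a parent-reported counterpart correlates 0.7 with the item, 60% of children have an earlier value, and predictors correlate 0.5. At earlier-value correlation 0.8 / 0.9 the further reduction is then 0.2 / 0.7% at 5% missing, 0.6 / 1.1% at 10%, 1.8 / 2.4% at 20% and 6.0 / 6.8% at 40%.

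**Step 5: which items have a counterpart.** Setting Table 2 beside Table 3, ROM, pain, FMS, GMFCS, physical training at school and recreational activities appear in both. Muscle tone, GMFM-66, stairs, bikes, orthosis and wheelchair appear only in Table 2. In the Activities block, three of the four CPUP predictors have no counterpart.

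**Step 6: the outcome in the imputation model.** Steps 1 to 4 include it, but the Missing data section does not name it. In the Step 1 design without the outcome and without the earlier value, the mean coefficient (truth 0.30) is about 0.24 at 20% missing and 0.17 at 40%. With the outcome it is 0.295-0.299 and 0.287-0.288. An earlier value correlated 0.9, still without the outcome, gives 0.28 and 0.27. Naming the outcome is therefore part of the same edit, and on a literal reading of the SAP it matters more.

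**The case against.** The strongest reply is that nothing here is an error. The latest registration is a coherent choice of predictor value, MICE with 100 imputations is standard, and the point contradicts no statement or number in the SAP. That stands, which is why this is offered as an improvement.

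The premise is also thinly documented. The SAP gives no item missingness, no number of registrations per child, and no sign that a child lacking an item now had it recorded before. The Background describes the programme, not these 78 children. The planned time bands, since dropped, ran to 25 months and more before the activity measurement. An earlier value may be older still, so a correlation of 0.8 to 0.9 in growing children cannot be taken for granted. This stands too, and the size is therefore only a conditional range.

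Same-child information may already be in the plan. If the imputation uses CPUP and questionnaire predictors together, parent-reported items partly do the work (Step 4). The point then survives mainly for the six items without a counterpart.

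A reader might infer more than the documents support:
- **That the SAP limits imputation to the planned predictors and discards earlier values.** It is silent: auxiliary variables are neither named nor excluded.
- **That the fix would win back part of the fall from 123 to 78 children.** Those 45 children (123 − 78) are lost because of incomplete CPUP registration, which this cannot repair.
- **That every incomplete CPUP predictor has a wider interval than necessary.** This is true only where some of the affected children have an informative earlier value.
- **That lasso inclusion proportions in Model 2a become noisier.** This is plausible, but it was not simulated.

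**Conclusion.** The point holds as a cheap, conditional improvement to the Missing data section. The direction is consistent: adding an informative earlier value lowered the SE or left it unchanged in every setting of Step 1. The size is small unless an item is often missing and stable over time. The top of the range (14%) needs 40% missing, correlation 0.9, earlier values for nearly all children and no questionnaire counterpart. At 5-10% missing the gain is a few per cent at most. Complete items and children without an earlier value gain nothing. All sizes rest on assumptions that the documents can neither confirm nor refute, and they were obtained for continuous items missing completely at random.

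**What to change.** Keep the latest registration as the analysis value and leave the predictors of Models 1a and 2a unchanged. In the Missing data section, add three statements:

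1. For each CPUP predictor incomplete at the latest registration, the child's most recent earlier recorded value of the same item enters that item's MICE equation as an auxiliary. It enters no other item's equation and neither analysis model. Where the earlier value is itself absent, it is imputed in the same chain.
2. Accelerometer counts are included in the imputation model. Children without outcome data are already excluded, so this column is complete.
3. The report gives, for each CPUP item, the number missing at the latest registration and how many of those children have an earlier value.

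The cost is a short SAP edit before the analysis and retrieval of earlier rows from the same registry, with no new data collection. The downside is a few extra, partly incomplete columns in a small-sample imputation; one auxiliary per incomplete item keeps that limited.

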## 8. Supplementary information

### SAP tables and figures

[figure not shown]

Figure 1. Flowchart of participants

Table 1. Participant characteristics

	Participants with CPUP data (n= )	Participants without CPUP data (n= )	Non-participants from CPUP (n= )
Age in years (mean (SD))			
At index date	xx (xx)	xx (xx)	xx (xx)*
Time in months from index date (mean (SD))			
To collection of questionnaire data	xx (xx)	xx (xx)	-
To collection of accelerometer data	xx (xx)	xx (xx)	-
To collection of CPUP data	xx (xx)	-	xx (xx)
Gender (n (%))			
Boy	xx (%)	xx (%)	xx (%)
Girl	xx (%)	xx (%)	xx (%)
Region of residence (n (%))			
Capital Region of Denmark	xx (%)	xx (%)	xx (%)
Central Denmark Region	xx (%)	xx (%)	xx (%)
Region of Northern Denmark	xx (%)	xx (%)	xx (%)
Region Zealand	xx (%)	xx (%)	xx (%)
Region of Southern Denmark	xx (%)	xx (%)	xx (%)
Cerebral palsy subtype (n (%))			
Spastic	xx (%)	-	xx (%)
Ataxic	xx (%)	-	xx (%)
Dyskinesia	xx (%)	-	xx (%)
Mixed/not classified	xx (%)	-	xx (%)
Missing data	xx (%)	-	xx (%)
GMFCS level (n (%))			
I	xx (%)	xx (%)**	xx (%)
II	xx (%)	xx (%)**	xx (%)
III	xx (%)	xx (%)**	xx (%)
Accelerometer count (mean (SD))	xx (xx)	xx (xx)	-

Abbreviations: GMFCS: Gross Motor Function Classification System, CPUP: Cerebral Palsy Follow-Up Program

Index date= date on which consent was given for participation, \*= the time of mass release of invitation to the study (November 3, 2020), \*\*=as reported by parents

Table 2. Prediction of physical activity using CPUP data predictive variables (Model 1a)

ICF constructs	Variables	Coef. [95% CI]	p-value	Adj.R 
Body Function & Structure				xx
	ROM	xx [xx,xx]	xx	
	Pain	xx [xx,xx]	xx	
	Muscle tone (modified Ashworth Scale)	xx [xx,xx]	xx	
	GMFCS level	xx [xx,xx]	xx	
Activities				xx
	FMS	xx [xx,xx]	xx	
	GMFM-66 score	xx [xx,xx]	xx	
	Ability to climb stairs	xx [xx,xx]	xx	
	Bikes	xx [xx,xx]	xx	
Participation				xx
	Participation in PT at school	xx [xx,xx]	xx	
	Participation in recreational activities	xx [xx,xx]	xx	
Personal Factors				xx
	Age	xx [xx,xx]	xx	
	Gender	xx [xx,xx]	xx	
	CP classification	xx [xx,xx]	xx	
Environmental Factors				xx
	Residence region	xx [xx,xx]	xx	
	Use of orthosis	xx [xx,xx]	xx	
	Use of wheelchair	xx [xx,xx]	xx	

Abbreviations: ROM: Range of motion; FMS: Functional Mobility Scale, PODCI: Pediatric Outcomes Data Collection Instrument; PT: physical training;

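### Models 2a and 2b select single columns by ordinary lasso but rank and report whole predictors, and the SAP has no rule for when a multi-level predictor counts as included

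*Combined protocol and SAP*

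**What the plan says.** Section 7, Regression models, specifies penalised regression by lasso for Model 2a, with "covariates as chosen by lasso to obtain an optimal fit from model 1a as predictive variables to determine which variables to retain", and for Model 2b, with "covariates as chosen by lasso to obtain an optimal fit from model 1b as predictive variables to determine which variables to retain". The Protocol deviations section repeats this. Neither place names a group penalty or a set of variables that stays in unpenalised.

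The Missing data section runs the lasso in each of 100 imputed data sets, after which "the predictors will be ordered by proportion of imputation sets in which they are included". It continues: "we will construct a final prediction model including all predictors included in at least 50% of the" imputation sets, with another cutoff allowed if an elbow plot looks convincing.

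The candidates stand in Tables 2 and 3. "Residence region" is in both, and Table 1 lists five regions. "CP classification" is in Table 2 only, and Table 1 lists four substantive subtypes. "Means of transport to school" is in Table 3 only, and its levels and coding are not given. Tables 4 and 5 are to look like Tables 2 and 3, restricted to the variables selected. The full predictor list is left to the protocol article.

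**The concern.** A nominal variable with k levels goes into a regression as k−1 columns (reference coding) or k columns (full indicator coding). Ordinary lasso decides on each column by itself. It can keep one region and drop the rest, and the variable as a whole has several chances to be picked up by noise where a continuous variable has one.

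The plan then ranks and lists at the level of the predictor. It never says how column decisions become a predictor decision, or whether the final model takes the whole variable or only the columns chosen. Inclusion proportions are therefore not comparable between region and, say, age. At stake are the predictor lists in Tables 4 and 5, which are the product of the secondary analysis. The counting rule would have to be chosen during the analysis, in addition to the flexible cutoff.

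**Working it through.** The SAP gives no selection probability or error rate for Model 2, so there is no planned figure to reproduce. The check sets out the two penalties and then simulates at the SAP's own sample sizes.

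**Penalties.** Ordinary lasso minimises RSS/(2n) + λ Σ_j |b_j|, summed over columns j. Group lasso minimises RSS/(2n) + λ Σ_g √m_g ‖b_g‖, summed over predictors g with m_g columns each, so a predictor enters or leaves whole.

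**Inputs from the SAP.** n = 78 for Model 2a (Study size: "only 78 of these children are eligible for analysis with CPUP data") and n = 123 for Model 2b (same section); region with 5 levels and CP classification with 4 (Table 1).

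**Assumed, not in the documents.** Independent predictors, complete data, penalty at the 10-fold cross-validation minimum; region shares .31/.23/.10/.14/.22; CP shares .85/.04/.06/.05; transport with 4 levels at .4/.3/.2/.1; true R² of 0, 0.3 or 0.5, carried by three continuous variables. Model 2a had 14 single-column variables plus CP classification and region; Model 2b had 15 plus transport and region. All nominal predictors were pure noise. There were 600 data sets per cell.

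**Results for a noise region.** It counts as entered if at least one level is selected. Ordinary-lasso ranges run over reference and full coding.

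| Model, R² | Lasso: region | Lasso: single-column noise | Ratio | Group lasso: region vs single |
|---|---|---|---|---|
| 2a, 0 | 18-21% | 7% | 2.6-2.9 | 11% vs 10% |
| 2a, 0.3 | 63-67% | 28-29% | 2.2-2.3 | 34% vs 31% |
| 2a, 0.5 | 70-72% | 30-33% | 2.1-2.4 | 38% vs 32% |
| 2b, 0 | 19-21% | 7-8% | 2.4-3.1 | 6% vs 8% |
| 2b, 0.3 | 69-70% | 28-30% | 2.3-2.5 | 31% vs 30% |
| 2b, 0.5 | 65-69% | 27-29% | 2.2-2.5 | 33% vs 30% |

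Ratios come from the unrounded rates within each coding; for example, Model 2a at R² = 0.3 with reference coding gives 0.633/0.294 = 2.15. The Monte Carlo standard error is at most about 2 percentage points for the nominal predictors.

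Noise CP classification (Model 2a) entered in 15-16%, 57-62% and 63-64% at R² = 0, 0.3 and 0.5, about twice the single-column rate. When a nominal predictor entered, only some of its columns were selected in 90-100% of cases.

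**Where the excess arises.** Each indicator column on its own had about the same chance as a single-column variable, or slightly less (5-8% at R² = 0; 23-33% at R² = 0.3-0.5). The excess comes from having several of them. If columns entered independently at 0.269, four would give 1 − (1 − 0.269)⁴ = 0.71; the simulated value was 0.63, because columns share one penalty and are correlated.

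**Sensitivity to the simulation set-up.** A smaller run at R² = 0.3 (about 95 data sets per n) gave region 74% (n = 78) and 63% (n = 123) against 30-34%; group lasso gave 40% and 35% against 33-35%. A third run (shares 30/23/11/15/21%, three true continuous predictors, 1500 data sets per n) gave 74% and 79% against 36-37%. Its group-lasso part, with only 135 and 139 data sets and a standard error of about 4 points, gave 45% against 31% at n = 78 and 32% against 37% at n = 123.

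**What each counting rule would do.**
- Any level counts, variable refitted whole: excess noise entry as tabulated, no pieces in the final model.
- Levels counted one by one: no advantage for a single level, but contrasts such as one region against all others can reach the final model.
- All levels required: nominal predictors are disadvantaged.

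**The case against.** The strongest reply is that the SAP never says columns are the retained unit. It speaks of predictors and variables throughout, so a selected variable may well be refitted whole. That stands. A reader might infer that region and CP classification will be favoured and will also enter the final models in pieces. The documents do not support this: the two harms arise under different counting rules, and a third rule reverses the first.

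Second, the percentages are frequencies across simulated samples, whereas the SAP's 50% refers to imputed versions of one sample. This stands too, and the table cannot be read against that cutoff. A limited simulation with the 50% rule (R² = 0.3, 10 imputations instead of 100, 15% missing in 8 of 14 continuous predictors, region fully observed, all assumed) suggests that the cutoff does not remove the problem. Noise region passed in 79% (n = 78) and 82% (n = 123) if any level counts and in 3% and 4% if all must, against 38% and 37% for a fully observed single-column noise variable.

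Third, the Exposure and adjustment variables section calls region and CP subtype covariates, so they might be forced in and escape selection. This has little support: the Regression models section speaks of covariates chosen by lasso, and Table 4 is to list only the variables selected.

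Fourth, a noise continuous variable itself enters in about 30% of samples at R² of 0.3-0.5. That part comes from the assumed penalty rule and not from coding; only the gap between the rates bears on this point.

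Two further inferences go too far. Transport cannot be called nominal with a known number of levels, and the SAP does not say that splines enter Model 2. The single coefficient row per nominal variable in Tables 2 and 3 is a table-shell matter and not an analysis error.

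**Conclusion.** The point holds as a mismatch between the unit of selection (column) and the unit of ranking and reporting (predictor), with no rule to connect them. It is certain for region in both models and for CP classification in Model 2a. It extends to any other predictor coded in several columns, for example GMFCS level as categories or FMS at three distances.

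If any level counts, a noise region enters about 2 to 3 times as often as a single-column noise variable: about 63-74% against 27-34% at R² of 0.3-0.5 (one run reached 79% against 36-37%), and 18-21% against 7-8% at R² = 0. The absolute rates depend on the assumed R², level shares and cross-validation rule; the ratio is more stable. The direction of the harm depends on the unstated counting rule. Model 2 is the secondary analysis, so the primary Model 1 is not affected, but the rule should be settled before the analysis is run.

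**What to change.** In Models 2a and 2b:

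1. State the coding of every predictor that takes more than one column, including means of transport.
2. Penalise all columns of such a predictor, and of any spline if used in Model 2, as one group with group-size weights (group lasso).
3. In the ranking across imputed data sets, count inclusion per whole predictor.
4. Enter all levels of a retained predictor in the final model and in Tables 4 and 5.

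The cost is a few sentences in the SAP and software beyond that named under Statistical software (an add-on package or R). No new data are needed. At n = 78 group lasso reduces the excess substantially but may not remove it (about 34-45% against 31-35% at R² of 0.3-0.5 and in the third run). If ordinary lasso is kept, whole-predictor counting with a whole-variable refit would keep pieces out of the final model, but under an any-level rule the excess entry would remain.
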